#### 9.1.4 Adverse events of special interest

Adverse events of special interest (AESI) are defined in protocol Section 7.2.5 as hypersensitivity reactions, convulsions, *clostridioides difficile*-associated colitis or pseudomembranous colitis, hepatic enzyme increased, hyponatremia, renal failure, infusion site reactions, and thromboembolic events. These AESIs will be identified using the following narrow Standardized MedDRA Query (SMQ) or MedDRA PTs:

- Hypersensitivity reactions (Narrow SMQ code 20000214)
- Convulsions (Narrow SMQ code 20000079)
- *Clostridioides (Clostridium) difficile*-related AEs (Narrow SMQ code 20000080)
- Hepatic enzyme increased (PTs: Hepatic function abnormal, Alanine aminotransferase, Alanine aminotransferase abnormal, Alanine aminotransferase increased, Aspartate aminotransferase abnormal, Aspartate aminotransferase increased, Hepatic enzyme abnormal, Hepatic enzyme increased, Liver function test abnormal, Liver function test increased, Transaminases increased)
- Hyponatremia (PTs: Blood sodium decreased or Hyponatraemia)
- Acute renal failure (Narrow SMQ code 20000003)
- Extravasation events (injections, infusions and implants) (Broad SMQ code 20000136)
- Embolic and thrombotic events (Narrow SMQ code 20000081).

Adverse events of special interest will be summarized by SOC and PT.

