### 1.2.3 Nonclinical toxicology

The toxicological profile of ceftobiprole was characterised in an extensive repeated-dose toxicity program that included systemic toxicity studies up to 13 weeks in rats, dogs and primates; reproductive toxicity; genotoxicity; local tolerability; and special studies to address the antigenic, phototoxic and nephrotoxic potential. In addition, juvenile toxicity was assessed in rats.

In rats, the primary targets of toxicity were the kidneys and the infusion site. Signs of vascular irritation at the IV infusion site were likely related to the large size of the catheter relative to that of the venous lumen. Vascular irritation by the test article was largely confined to the region of the vein damaged by the catheter, with little or no effect distal to the infusion site where the vein was exposed to the test article but not to the catheter. Toxicity to the kidneys was observed at doses  $\geq 250$  mg/kg, and was associated with the precipitation of drug-like material in the distal part of the nephron.

In dogs, reddening of the skin and mucous membranes was attributed to histamine release. No other relevant findings were observed.

In marmosets, thromboembolic effects secondary to infusion site reactions were observed, including thrombus formation at the catheter tip. Signs of vascular irritation at the IV infusion site were consistent with respective effects noted in rats, and were likely related to technical challenges inherent to chronic IV dosing in small animals. Findings in the kidneys were reversible and not associated with microscopic lesions. There were no indications of kidney toxicity related to precipitation as seen in rats.

Ceftobiprole medocaril was neither teratogenic nor embryotoxic in rats or cynomolgus monkeys, and had no effect on fertility and early embryonic development in rats. In a pre- and post-natal development study in rats, slight maternal toxicity was seen at high doses, but there were no direct effects on pups.

No mutagenic potential was seen in the Ames test or in the Chinese hamster ovarian assay.

Ceftobiprole medocaril exhibited low irritancy potential in rabbit local tolerance studies. No phototoxic potential was seen, and no hemolysis or precipitation was observed at concentrations  $\leq 1.25\%$ .

The toxicity of ceftobiprole medocaril in neonatal and juvenile rats was investigated in a study with 7-week once daily subcutaneous administration starting on Day 1 post-partum.

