### 7.2.5 Adverse events of special interest

An adverse event of special interest (AESI) is defined as a serious or non-serious AE that is of scientific and medical concern specific to the sponsor's product for which ongoing monitoring and rapid communication by the investigator to the sponsor can be appropriate. The following are considered AEs of special interest for the purposes of this study, based on nonclinical data and the known safety profile of ceftobiprole or the cephalosporin class of antibiotics, and are to be promptly reported in the eCRF, along with an assessment of relationship by the Investigator:

- Hypersensitivity reactions
- Convulsions
- *Clostridioides difficile*-associated colitis or pseudomembranous colitis
- Hepatic enzyme increased
- Hyponatremia
- Renal failure
- Infusion site reactions
- Thromboembolic events

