### 9.1 Adverse events

Adverse events are defined in protocol Section 7.2. As the definition includes only events which occur after first study-drug administration, all AEs are considered to be ‘treatment emergent’. Pre-treatment events are reported as medical history. Relationship and action taken referring to ampicillin and aminoglycoside are listed only.

An overview summary of number and percentage of patients will be provided for any AE, study-drug-related AEs, SAEs, study-drug-related SAEs, AEs leading to treatment discontinuation, study-drug-related AEs leading to treatment discontinuation, AEs leading to treatment interruption / dose reduction, study-drug-related AEs leading to treatment interruption / dose reduction, AEs leading to death, study-drug-related AEs leading to death, AEs of special interest (see Section 9.1.4), and study-drug-related AEs of special interest will be provided.

All AEs, SAEs, and AEs leading to death will be presented in separate listings.

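### AESIs are identified only by coded searches whose infusion-site and renal categories do not match the protocol's, with no route for events the investigator identified as AESIs

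*SAP*

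**What the plan says.** Protocol Section 7.2.5 lists eight AESI categories. One is "Infusion site reactions", without restriction to any mechanism, and another is renal failure, without restriction to acute onset. Events in these categories "are to be promptly reported in the eCRF, along with an assessment of relationship by the Investigator".

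SAP Section 9.1.4 repeats the eight categories and then gives one way of finding them: "These AESIs will be identified using the following narrow Standardized MedDRA Query (SMQ) or MedDRA PTs". In the place of infusion site reactions the list has "Extravasation events (injections, infusions and implants) (Broad SMQ code 20000136". In the place of renal failure it has "Acute renal failure (Narrow SMQ code 20000003".

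Two outputs depend on this set. Section 9.1.4 states that "Adverse events of special interest will be summarized by SOC and PT". The overview table in Section 9.1 has lines for "AEs of special interest (see Section 9.1.4), and study-drug-related AEs of special interest", defined by reference to the same section.

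SAP Section 12 states that the protocol-defined analyses are unchanged. The only clarification it records concerns the Clinically Evaluable population.

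**The concern.** The AESI list is the sponsor's own statement of which events deserve separate attention, so the AESI table should count the categories that the protocol names. For two categories the SAP searches under another name. For infusion site reactions that name describes a different concept; for renal failure it describes a narrower one. The SAP gives no reason for either change and does not record them in Section 12.

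There is also no fallback. An investigator may recognise an infusion site reaction and report it as the protocol asks. If the verbatim term then codes to a PT outside the query, nothing in the plan brings the event into the AESI count. The SAP provides neither for using the investigator's identification nor for a medical review of the search result.

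The two affected categories are not incidental. Protocol Section 1.2.3 reports: "In rats, the primary targets of toxicity were the kidneys and the infusion site". The same section attributes much of the vascular irritation to catheter size and reports low irritancy in rabbits, so this explains why the category is on the list and is not evidence of a hazard. Protocol Section 4.4 also names infusion site reactions among possible reasons for withdrawal.

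**Working it through.** The plan contains no figure to reproduce. The check is a comparison of the two lists, then a statement of scale.

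**Step 1: categories against searches.**

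| Protocol 7.2.5 | SAP 9.1.4 search | Match by name |
|---|---|---|
| Hypersensitivity reactions | Narrow SMQ | Yes |
| Convulsions | Narrow SMQ | Yes |
| *C. difficile* or pseudomembranous colitis | Narrow SMQ, *C. difficile* events | Close |
| Hepatic enzyme increased | 11 listed PTs | Yes |
| Hyponatremia | 2 listed PTs | Yes |
| Renal failure | Narrow SMQ, acute renal failure | Narrower |
| Infusion site reactions | Broad SMQ, extravasation events | Different concept |
| Thromboembolic events | Narrow SMQ, embolic and thrombotic events | Yes |

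That makes five narrow SMQs, one broad SMQ and two PT lists. The lead-in mentions narrow SMQs and PTs only, so it does not describe the infusion-site entry.

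**Step 2: routes into the AESI set.** The only stated route is a search hit. Protocol Section 7.2.5 requires eCRF reporting, but the AE-page contents in Protocol Section 7.4.3.1 do not include an AESI field. Whether an investigator flag exists as data is therefore unknown.

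**Step 3: where a missed event still appears.** SAP Section 9.1.1 tabulates all AEs by System Organ Class (SOC) and PT, and drug-related AEs separately. Sections 9.1.2 and 9.1.3 add tables by relationship and severity. Section 9.1 lists every AE. Only the AESI lines of the overview and the AESI table lose the event.

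**Step 4: other sources for the same finding.** Creatinine, sodium, ALT and AST are mandatory at screening and end of treatment (Protocol Table 4) and enter shift tables (SAP Section 9.3). Renal, sodium and hepatic changes therefore have a second, tabulated route. Infusion site reactions have no laboratory counterpart, and SAP Section 9.2 only lists physical examination results.

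**Step 5: scale of one infant.** The planned numbers are 8 overall, 6 pre-term and 2 term (SAP Section 4.1). They are minimums, but Protocol Section 4.6 stops enrolment to each group when its minimum is reached.

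- Overall: 1/8 = 12.5 percentage points
- Pre-term: 1/6 = 16.7
- Term: 1/2 = 50

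An infant drops out of the any-AESI line only if none of that infant's other events is a search hit. If this were the only AESI, the line would read 0, with its percentage suppressed under SAP Section 4, where it should read 1 (12.5%).

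For scale only, since the plan has no intervals, the exact 95% interval for 0/8 runs from 0 to 1 − 0.025^(1/8) = 36.9%. For 1/8 it runs from 0.3% to 52.7%. The intervals overlap widely, so the matter is correct description of individual infants, not the precision of a rate.

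**The case against.** The strongest reply is that nothing leaves the safety report. Every AE is tabulated under its own PT and listed, and with about eight patients each line can be read. That is correct, and it limits the point to two outputs. A reader might infer that events are lost from the safety analysis or that the primary endpoint is distorted; the documents do not support this. SAP Section 3.2.1 names AEs, SAEs, deaths, discontinuations due to AEs, laboratory tests, vital signs and physical examination. AESIs are not a named component and enter only as AEs, all of which are counted.

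A reader might also infer that the SAP overrides investigators' reports and can only lose events. That goes too far. The searches run on the AEs that investigators reported, and they can add events that no investigator recognised as AESIs. Searching alone can only lose events relative to a rule that uses both sources. No AESI flag is shown that could be overridden.

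Third, the broad extravasation query may already contain many infusion-site terms. Its title mentions infusions, and it is the only query set to broad, which fits an intention to widen it. The documents do not give its contents, so this can be neither confirmed nor excluded.

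Fourth, renal impairment is excluded at entry (Protocol Section 4.3, criterion 7) and participation lasts about 5–7 weeks, so new renal failure would ordinarily be acute. The practical effect of the renal wording is probably small.

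Finally, the narrow/broad conflict is editorial, because the entry gives both scope and code. The mismatch in category names and the absence of a fallback remain.

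**Conclusion.** The point holds as a mismatch between the protocol's AESI categories and the SAP's counting rule. Infusion site reactions are searched for under the name of a different concept, renal failure under a narrower one, and no step catches a qualifying event that codes outside the searches. Section 12 does not mention the remapping. Protocol Section 8.4.1.1 specifies no AESI table, so what goes unrecorded is a change in category definition, not the replacement of a protocol-specified table.

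The consequence is confined to the AESI lines of the overview and the AESI table by SOC and PT. One infant wrongly absent from the any-AESI line is 12.5 points overall, 16.7 in pre-term and 50 in term infants, assuming enrolment stops at eight and the infant has no other AESI hit. No number of missed events or terms is claimed, because the SMQ contents are not in the documents. The point rests only on the category names and on the absence of a fallback.

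**What to change.** In SAP Section 9.1.4, before database lock:

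- Keep the existing searches. For infusion site reactions, add all PTs naming an infusion, injection or catheter site reaction.
- Define the AESI set as the union of search hits and events that the investigator identified as AESIs. If the eCRF has no AESI field, replace the second part with events found by a documented review of the AE listing against the eight protocol categories, completed before lock.
- Correct the lead-in so that it allows for the broad query.
- Align the renal category with the protocol.
- List the source of each AESI: search, investigator or review, or more than one.

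The cost is minor SAP wording, a small programming change and, where there is no eCRF field, one review of a short listing. No new data collection is needed. The AESI count may come out slightly higher than under the searches alone.

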#### 9.2 Physical examination

Physical examination results for all patients will be presented in a listing.

#### 9.3 Clinical laboratory evaluations

Local laboratory tests include hematology, blood chemistry, and urine analysis (dipstick) parameters in accordance with the protocol Schedule of Assessments and protocol Table 4.

Summary tables for laboratory parameters including actual values and change from baseline values will be presented for mandatory laboratory parameters with numeric values by visit.

Laboratory data will also be summarized using shift tables where appropriate. Each patient's continuous laboratory safety parameter values will be flagged as 'low', 'normal', or 'high' relative to the normal ranges of the laboratory. Each patient's categorical laboratory safety parameter values will be flagged as 'abnormal' or 'normal'. These categorical data will be summarized in shift tables comparing the minimum post-baseline value, maximum post-baseline value, and all other relevant post-baseline visits, with those at the baseline visit.

Laboratory data collected at unscheduled visits will be included in listings, and will contribute to tables of shifts from baseline and tables showing changes from baseline to

---

highest value and lowest value. Unscheduled laboratory results will not be windowed for the purposes of assigning a nominal visit.

All clinical laboratory parameters will be presented in a listing including normal ranges, and indicating if the value is out of range.

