#### **4.3 Exclusion criteria**

Patients who meet any of the following criteria must be excluded from the study:

1. History of a previous clinically relevant hypersensitivity or serious adverse reaction to beta-lactam antibiotics, or to aminoglycosides if intended to be used in combination with ceftobiprole
2. Viral, fungal, or parasitic pathogen as the sole reason for infection, OR known resistance of the causative bacterial pathogens to ceftobiprole
3. Refractory septic shock not responding to 60 minutes of vasopressor treatment within 48 hours before enrollment
4. Proven ventilator-associated pneumonia
5. Proven central nervous system infection (e.g., meningitis, brain abscess)
6. Proven osteomyelitis, infective endocarditis, or necrotising enterocolitis
7. Impaired renal function or known significant renal disease, as evidenced by an estimated glomerular filtration rate (using the Schwartz formula or other applicable formula) calculated to be less than 2/3 of normal for the applicable age group, OR urinary output  $< 0.5 \text{ mL/kg/h}$  (measured over at least 8 hours), OR requirement for dialysis
8. Significant laboratory abnormalities, including:
  - a) Hematocrit  $< 20\%$
  - b) Absolute neutrophil count  $< 0.5 \times 10^9/\text{L}$
  - c) Alanine aminotransferase (ALT) or aspartate aminotransferase (AST)  $> 8 \times$  the age-specific upper limit of normal
9. Progressively fatal underlying disease, or life expectancy  $< 30$  days
10. Documented history of convulsions

11. Severe immunodeficiency (congenital or acquired)
12. Use of systemic antibacterial therapy for longer than 72 hours within 7 days before start of study medication
13. Any condition including antepartum / peripartum factors or procedures, which would, in the opinion of the Investigator, make the patient or caregiver unsuitable for the study, putting the patient at risk or compromising the quality of the data
14. Participation in another clinical study with an investigational product within 30 days of enrollment in the current study

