#### Conclusion

Serum creatinine levels are generally used to monitor renal function ([CHMP-PDCO 2009](#)). Glomerular filtration rate (GFR) is indirectly proportional to serum creatinine, i.e., a GFR of two-thirds of normal corresponds to a 1.5-fold greater than normal serum creatinine level. Since post-menstrual age is the best parameter of kidney maturation, the following creatinine thresholds (determined with the enzymatic method) may be used to support the evaluation of Exclusion criterion [7](#):

Post-menstrual age (weeks)	Creatinine (mg/dL)	Rationale
28 – 34 completed	1.32	150% of the upper limit of the laboratory normal ranges
35 – 42 completed	1.10	Arithmetic mean of 1.32 and 0.88
$> 42$	0.88	Upper limit of the laboratory normal ranges of the lower age groups and slightly more than 150% of $0.5 \text{ mg/dL}$ , the stable creatinine level during the first 2 years of life

Considering these serum creatinine thresholds, a GFR estimated with the modified Schwartz formula of less than the values given below might provide evidence of impaired renal function or known significant renal disease:

Length (cm)	eGFR threshold (mL/min/1.73 m  )		
	Post-menstrual age (weeks)		
	28 – 34 completed	35 – 42 completed	> 42
33	10.3	12.4	15.5
34	10.6	12.8	16.0
35	11.0	13.1	16.4
36	11.3	13.5	16.9
37	11.6	13.9	17.4
38	11.9	14.3	17.8
39	12.2	14.6	18.3
40	12.5	15.0	18.8
41	12.8	15.4	19.2
42	13.1	15.8	19.7
43	13.5	16.1	20.2
44	13.8	16.5	20.7
45	14.1	16.9	21.1
46	14.4	17.3	21.6
47	14.7	17.6	22.1
48	15.0	18.0	22.5
49	15.3	18.4	23.0
50	15.6	18.8	23.5
51	16.0	19.1	23.9
52	16.3	19.5	24.4
53	16.6	19.9	24.9
54	16.9	20.3	25.3
55	17.2	20.7	25.8
56	17.5	21.0	26.3
57	17.8	21.4	26.8
58	18.1	21.8	27.2
59	18.5	22.2	27.7
60	18.8	22.5	28.2

Investigators will exercise their clinical knowledge in conjunction with these thresholds when determining the applicability of Exclusion criterion 7 to potential participants in the study.

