## 4.1 Sample size justification

This study is not powered for inferential statistical analysis. The sample size (eight patients; two term and six pre-term) is considered adequate to evaluate the safety of ceftobiprole in neonates and infants aged  $\leq 3$  months with LOS.

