#### 4.3.3 Study day calculation and visit windows

Visit windowing approaches will not be used for this study, and visit-based summaries will include scheduled assessments only. If more than the specified number of measurements has been taken in a scheduled visit, the latest recorded values will be used in visit summaries, unless otherwise stated. All scheduled and unscheduled post-baseline assessments will be used for derivation of minimum and maximum post-baseline values. If more than one assessment has the same minimum or maximum value, then the record with earliest occurrence will be selected respectively as the minimum or maximum assessment.

The following conventions will be used to calculate analysis study day:

- Day 1 is the day of first study drug administration. Day -1 is the day before Day 1. No Day 0 is defined for this study.
- Prior to Day 1, the algorithm is:  
Study Day = visit/examination date – date of first study drug administration
- For Day 1 and subsequent days, the algorithm is:  
Study Day = visit/examination date – date of first study drug administration + 1.

Summary data such as AEs and concomitant medications will not be reported by visit. Tables that report abnormalities (e.g., clinically-notable abnormalities, laboratory shift tables) will include all assessments.

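### Where normal ranges change with the infant's age, the minimum and maximum laboratory shift rows can read normal for an infant who had an out-of-range value; define these rows by flag (minor)

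*SAP*

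**What the plan says.** SAP 9.3 classes each continuous laboratory value as low, normal or high "relative to the normal ranges of the laboratory". It continues: "These categorical data will be summarized in shift tables comparing the minimum post-baseline value, maximum post-baseline value, and all other relevant post-baseline visits", with baseline as the comparator.

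SAP 4.3.3 states how the extreme records are found. "All scheduled and unscheduled post-baseline assessments will be used for derivation of minimum and maximum post-baseline values". If several records share the extreme value, "then the record with earliest occurrence will be selected respectively as the minimum or maximum assessment". Neither section consults the range or the flag when choosing the record, and neither adds a row for the worst flag. Protocol 8.4.1.1 promises change from baseline to the overall worst post-baseline value, without saying whether worst is judged on the raw value or against a range.

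Other text bears on the point:

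- SAP 4.3.3 restricts visit-based summaries to scheduled assessments, but also says that laboratory shift tables include all assessments.
- SAP 9.3 says unscheduled results contribute to the shift tables and are not assigned to a nominal visit. It also provides a listing of every value with its range and an out-of-range mark.
- Protocol Table 3 (footnote 9) and Table 4 make the laboratory panel mandatory only at screening and EOT. Other samples are taken when clinically indicated.
- The protocol treats limits in this population as age-dependent. Exclusion criterion 8 for ALT and AST refers to "the age-specific upper limit of normal", and the creatinine table in Appendix 1 refers to "Upper limit of the laboratory normal ranges of the lower age groups".

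**The concern.** The flag of the lowest or highest raw value equals the infant's worst flag only if one range applies to all of that infant's post-baseline samples. Infants here enter from day 3 of life, many of them pre-term, and can be sampled over several weeks. If a laboratory uses age-banded ranges, the range can change between two samples.

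If a lower limit falls with age, an early Low can be displaced by a later, smaller value that is normal for its date. If an upper limit falls with age, a later High can be displaced by an earlier, larger value that was normal. The flagged value is not relabelled; another record takes its place in the row.

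Laboratory tests are part of the primary safety endpoint, and renal failure and raised hepatic enzymes are adverse events of special interest. A creatinine that fails to fall as expected is a case where the later, smaller value is the abnormal one. With the planned minimum of eight infants (two term, six pre-term), one misplaced infant is 1/8 = 12.5% overall, 1/6 = 16.7% of the pre-term group or 1/2 = 50% of the term group.

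**Working it through.** No sample-size or power calculation bears on this; the SAP states that "This study is not powered for inferential statistical analysis". The check applies the SAP rule and a flag-based rule to the same records.

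**Inputs.** The only age-banded laboratory figures in the documents are the creatinine thresholds in Protocol Appendix 1: 1.32, 1.10 and 0.88 mg/dL at post-menstrual ages 28–34, 35–42 and above 42 weeks. The figures are internally consistent: (1.32 + 0.88)/2 = 1.10, and 0.413 × 40/1.32 = 12.5, as in the eGFR table at 40 cm. They are eligibility thresholds, not a laboratory's range. Since 1.32/1.5 = 0.88, the first and last can both be built from a single upper limit. They serve below only as a stand-in for an age-banded upper limit.

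**Rules.** SAP rule: take the record with the largest value, the earliest if tied, and report its flag. Flag rule: report High if any post-baseline value is High.

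| Case | First post-baseline value | Second post-baseline value | SAP maximum row | Flag rule |
|---|---|---|---|---|
| a | 1.25 at 34.7 weeks (limit 1.32, normal) | 1.15 at 35.9 weeks (limit 1.10, High) | normal | High |
| b | 1.15 at 34.7 weeks (normal) | 1.15 at 35.9 weeks (High) | normal (tie goes to earlier) | High |
| c | 1.05 at 42.7 weeks (limit 1.10, normal) | 0.95 at 44 weeks (limit 0.88, High) | normal | High |
| d | 1.05 at 35.5 weeks (normal) | 1.15 at 36.5 weeks (same band, High) | High | High |
| e | 1.25 at 34.7 weeks (normal) | none | normal | normal |

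The rules differ only when two post-baseline values fall under different limits. The documents give no lower limits, so the Low direction follows by the same logic but cannot be illustrated with their figures.

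**How much the size depends on assumptions.**

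1. Assume a flat grid of value pairs, 0.50 to 1.59 mg/dL in steps of 0.01 (110 × 110 = 12,100 pairs), one value either side of a step. A High is displaced when the second value is above the new limit and the first is at least as large but not above the old limit. That is 22 + 21 + … + 1 = 253 pairs at either step.
   - Step 1.32 to 1.10: pairs with any High = 12,100 − 83 × 61 = 7,037; displaced 253/7,037 = 3.6%.
   - Step 1.10 to 0.88: pairs with any High = 12,100 − 61 × 39 = 9,721; displaced 253/9,721 = 2.6%.
2. Assume a uniform grid of gestational age 24–41 weeks and post-natal age 3–90 days. The share crossing the 35- or 43-week step is 2.8% over 2 days, 12.7% over 9 days, 18.2% over 13 days and 36.2% over 27 days. The last runs from Day 1 to the latest test-of-cure (TOC) visit, Day 14 + 14 = Day 28. These spans start at Day 1, so they overstate crossing between two post-baseline samples.
3. Take the top of both, and assume every infant has two post-baseline values and a High: 0.362 × 0.036 = 1.3%, or about 0.1 of an infant in eight.
4. A different assumption gives a very different answer. Take haematocrit with mean 44% then 37%, between-infant SD 4–5, within-infant SD 2–3, and every infant sampled either side of a boundary. The share of Low infants missed in the minimum row runs from about 3% (assumed lower limit 40% then 36%) to about 72% (42% then 31%). None of these inputs is in the documents.

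Items 1 to 4 show that the result is set by the assumed ranges. They do not estimate a frequency for this trial.

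**The case against.** The strongest reply is that little is at stake. With about eight infants and no hypothesis test, the listing lets every out-of-range value be read patient by patient. Clinically significant abnormalities are also recorded as adverse events, and several are summarised as events of special interest. An infant with only the mandatory EOT sample cannot be affected. The table shells that SAP section 4 mentions may settle the row layout. All of this stands and limits the priority. It does not make the row correct: a listing does not repair a wrong count in a summary table, and Protocol 7.4.3.1 makes an abnormal result an adverse event only if listed criteria are met.

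A reader might infer stronger conclusions that the documents do not support:

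- **That the flag disappears from the report.** It does not. It remains in the listing and, if scheduled, in the row for its visit. A Day 2 or TOC value, for example, belongs to a named visit.
- **That an unscheduled flag can appear in no shift row, or that the minimum and maximum rows are the only shift rows using unscheduled values.** This is one reading of unclear text. SAP 4.3.3 says that shift tables include all assessments. What is missing is a statement of which other row would carry an unscheduled value.
- **That a substantial share of abnormal infants is missed.** No laboratory range is given, and any percentage reflects assumed limits.
- **That Appendix 1 shows laboratory upper limits falling by 17–20% at each step.** The thresholds do fall by that much (1.10/1.32 = 0.83; 0.88/1.10 = 0.80), but they are eligibility cut-offs and do not show a step in a laboratory's normal range.

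**Conclusion.** The point holds as a minor defect in a derivation rule. As written, SAP 9.3 with 4.3.3 can show normal in the minimum or maximum shift row for an infant who had a Low or High. This requires that the laboratory's range changes with age between samples, and that a more extreme or earlier equal value was normal on its own date. When a flag is displaced in this way, the row understates abnormality.

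It needs at least two post-baseline values under different ranges. Because only EOT is mandatory after baseline, it should be uncommon, although infants with extra clinically indicated samples may be those of most safety interest. The conclusion assumes that at least some site laboratories report age-banded ranges. The protocol's own references to age-specific limits make that reasonable, but the ranges are not in the documents. Protocol 5.5.4 keeps each site with one laboratory, so a change of range within an infant would come mainly from age. The frequency in this trial cannot be estimated.

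**What to change.** In SAP 9.3, define the worst-case shift categories by flag: any post-baseline Low and any post-baseline High. Derive them over all scheduled and unscheduled values, each judged against the laboratory range applicable to the infant on the sample date. Keep the raw minimum and maximum, with the SAP 4.3.3 tie rule, for the numeric change-from-baseline summaries. This also states where an unscheduled out-of-range value enters the shift table.

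The cost is one sentence in the SAP and minor programming. No new data are needed, because values and ranges are already collected for the listing. Where an infant's ranges do not change, an infant counts as Low or High under the new rule exactly when the minimum or maximum row would have said so.
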